***Fitness Assessment Session-before and after the training program***

- Measurements of height, weight, body composition (percent body fat), temperature and blood pressure. The PERC/ICTS staff has extensive experience in these measurements in children and great care is expended in stadiometer and scale calibration and use.
- Children will be asked to fill a standard self-assessment Tanner staging questionnaire; this questionnaire is currently used by our group in several UCI IRB approved studies, and a copy is appended to this application.
- Dual X-ray Absorbiometry (DXA) – Each participant will have to perform 2 DXA assessments: 1 DXA in week 1, prior to beginning the training sessions, and 1 DXA in week 12, after completion of 10 week training. For each DXA, subjects will undergo a total of 3 scans: a complete body scan, a hip scan, and spine scan. Total and regional body composition will be measured by dual-energy X-ray absorptiometry (DXA) using a Hologic densitometer. Measurement of body composition using DXA is based on the exponential attenuation due to absorption by body tissues of photons emitted at two energy levels (40 and 70 keV). Subjects will be asked to lie on their backs on a padded table wearing normal clothes with metal objects removed. The counter moves in a raster pattern above the subject's body from head to foot and counts attenuation rates of photons emitted from the X-ray source within the table. The total dose for a scan is less than several hours of background exposure (1-4 millirem per DXA scan). DXA provides estimates of the following parameters: bone mineral densities (BMD; g/cm^2), soft-tissue attenuation ratios, fat and lean tissue weights (g), and bone mineral weight. These parameters can be recorded for the whole body or in any number of defined anatomical regions of interest. DXA scanning involves x-ray dose at minimal levels. Technicians do not wear shielding, nor do subjects require shielding during the procedure. Female subjects capable of having children (regardless of age) will be asked to provide a small urine sample prior to the DXA scan. Results of the pregnancy test will be disclosed to either the parent or the legal guardian with the child's permission and/or the participant for subjects less than 18 years of age. Results of the pregnancy test will be disclosed to female subjects 18 years of age or older.
- Exercise testing will be performed at the UCI PERC/ICTS Applied Physiology/Human Performance Core Laboratory. To measure cardiorespiratory responses to exercise and assess fitness, we will use a ramp-type progressive exercise test on an electronically braked cycle ergometer (SensorMedics Ergoline 800S, Yorba Linda, CA) (1), through a method previously designed for children and adolescents (2). The work rate will increase by 10 W per min (or adjusted according to the subject's age and fitness level) so that the total exercise time will roughly equal 8-12 min, and each subject will exercise to the limit of his or her tolerance. During the exercise, the participant will breath through a mouthpiece, a noseclip will be worn, and measurements of their breath will be taken. Gas

exchange will be measured breath-by-breath using a metabolic cart (SensorMedics VMax 229, Yorba Linda, CA). The metabolic cart measures inhaled as well as exhaled carbon dioxide and oxygen by use of a mouthpiece and noseclip allowing gas exchange measures in the breath. After exercise, participant's heart rate will be monitored until it reached pre-exercise values. If any faintness or dizziness is reported, participants are asked to lay down and are then allowed to leave after 30-min of cessation of symptoms. Gas exchange will be measured breath-by-breath (3). Multiple Pulmonary Function Tests (PFT's) will be performed prior to and following the exercise challenge. This approach has been used extensively in our laboratory in children, adolescents and adults.

- Diet: During the week of physical activity evaluation, participants will complete a three-day food record, to be analyzed by the UCI PERC bionutrition using the Nutrition Data System for Research (University of Minnesota, Minneapolis, MN), a specialized software containing a nutrient profile of over 18,000 foods.

### ***Exercise Challenge Session and Blood Draws--before and after the training program***

*The trainers are aware that they are responsible for the children's safety. All parents will be strongly encouraged to attend the training session with their child. The trainer is aware of abuse reporting procedures.*

- The exercise session will occur no less than 48 hours and no later than 4 weeks apart from the **Fitness Assessment Session**. Participants will arrive in the morning after an 8 hour fasting. Participants will be able to continue to use their long-term asthma control medications during the period in which they are required to fast. An indwelling catheter will be placed in an antecubital vein of each subject by trained physicians and/or nurses with specific experience in pediatric procedures of this nature. If requested, a cream will be used to numb the site for the catheter placement to reduce discomfort. The indwelling catheter will allow multiple blood draws without the possible adrenergic stimulation associated with multiple needle sticks.
- After a 20 min rest, PFTs and baseline blood draw will be acquired and exercise can begin. Exercise will consist of a series of 10, 2-min bouts of constant work rate cycle ergometry with 1-min resting intervals between each exercise bout. The work rate will be individualized for each subject, and equivalent to the work rate corresponding to 50% of the difference between the anaerobic or lactate threshold (LT--determined non-invasively from the ramp test) and peak VO2. We use this approach to ensure that the exercise input is standardized to physiological indicators of each individual subject's exercise capability.
- During exercise and for the 60 min following exercise additional blood samples will be acquired. The total amount of blood withdrawn at each timepoint will be up to 80 ml, or ~ 5 tablespoons for children and up to 160 ml for adults (no more than 5ml/Kg), amounts we routinely collect in children and adults without causing discomfort. If any faintness or dizziness is reported, participants are asked to lay down and are then allowed to leave after 30-min of cessation of symptoms. Collected blood samples will be analyzed for glucoregulatory hormones, pro-/anti-inflammatory cytokines, growth factors, markers of oxidative stress, gene and microRNA expression studies and leukocytes functional assays.
- Assessment of Exhaled NO: Participants will be asked to blow for approximately 5 seconds before and after exercise for analysis of the composition of expired gases found in the breath. As noted, our Co-Researcher has extensive experience in the measurement of NO in the exhaled breath in healthy controls and asthmatics. Assessment of exhaled breath NO represents a novel and exciting approach toward understanding airway inflammation.

Whenever exercise tests are being conducted on participants with asthma, there is always a licensed physician present at the center. Should a participant experience an asthma attack during the exercise testing, the participants will respond as they have been prescribed by their personal

physician. As a precaution, the on-site physician will be the one to provide the order for the bronchodilator (if need) before it is administered to the participant.

### **Measurement of Endothelial Function- Blood Flow Measurements**

Both visits described above will make use of a variety of non-invasive optical measurements of endothelial/vascular function and tissue oxygenation. These measurements are described below, and will take place during both fitness and a second exercise challenge sessions.

- A non-invasive measurement of endothelial function (blood flow and level of blood oxygenation measurements) will be performed with a modified hyperemic test. This is a very simple procedure in which a laser doppler sensor is applied to the volar aspect of the hand, at the 1st finger distal metacarpal surface. The cuff of a blood pressure machine is then placed around the wrist, and a computer-controlled manometer inflates the cuff to 200 mmHg, and then rapidly releases it. After the cuff is deflated, blood flow in the hand transiently increases, and the characteristics of this increases in flow (amount of peak flow, rapidity to reach this peak, etc.) are related to the health of the vascular system, and can be accurately measured by the laser doppler sensor. This measurement will occur during testing at the PERC/ICTS Exercise Lab, but NOT during exercise.
- An additional measurement modality we will use is Laser Speckle Imaging (LSI). This is a device that has been developed at the Beckman Laser Institute, and it consists of a non-contact single-wavelength light source coupled to a CCD camera. The laser will be projected on the participant's hand, and the reflected light will be collected by the camera. Using this technique, we will be able to record and analyze local heterogeneities in blood flow in the skin microcirculation. This data will be compared to the results obtained by the laser doppler sensor. This measurement modality will only be used at Beckman Laser Institute, and NOT during exercise
- In addition to the Periflux system, we will perform measurements of tissue content of hemoglobins, water, and lipids using Diffuse Optical Spectroscopy (DOS), a system developed at the Beckman Laser Institute of UC-Irvine. This instrument uses light in the near-infrared range of wavelengths to measure tissue optical properties in a safe, non-invasive manner. The pulse oximeter is a similar commercial instrument that has found wide clinical acceptance. This optical device uses two wavelengths, one red and the other near-infrared, to measure the arterial hemoglobin saturation (SaO2) of blood. DOS probe will be placed on the volunteer's upper extremity, lower extremity, or abdomen for a short duration (less than 5 minutes) before, during, and after exercise. DOS will be used to monitor tissue optical properties both during exercise testing (on the upper extremity, lower extremity, or forehead) at the PERC/ICTS Exercise Lab, and in static conditions at BLI (on the arm, leg, or abdomen).
- Body composition (% body fat) will be assessed via portable bioelectrical impedance assessment (InBody720), a commonly used method for estimating body composition, and in particular body fat. This portable device requires the subject to stand on the machine while measures of body mass, percent body fat and lean body mass are being done. Age and height will be inputted into the machine, followed by a 2-minute analysis in which the child simply stands on the machine.
- There are two devices that will be used that are considered DOS devices. One is the above-described BLI-fabricated device. Another is the TRS-20, developed by Hamamatsu Photonics. It works on similar principles, and will be used in the same way as described above.

### **Training Sessions**

Training will continue in community venues and in the Pediatric Exercise Research Center with professional personal trainers with a minimum of Bachelor degree in a Wellness/Exercise Science related field, P.E teachers or personal trainers certified by an accredited fitness

organization such as ACSM, NSCA, NASM or ACE. The training sessions will occur three times a week up to 10 weeks, in small groups of 3-6 subjects.

Those who participate in this study will have been cleared to participate in all sports, including school P.E. and extramural sports such as club soccer and basketball. In schools, children with asthma must have a release form for the use of a bronchodilator use when needed. These medicines can be determined by school officials. Increasingly, schools are permitting students to carry medication themselves.

The parent/legal guardian of the child participant will be instructed to bring his/her child's bronchodilator with them to the exercise training session (for adult participants, they will be instructed to bring their bronchodilator to the exercise training session). Before each training session begins, the trainer will ensure that the participant has his/her bronchodilator readily available prior to beginning exercise activities. Should an exercise-induced bronchoconstriction episode occur, participants will be instructed to respond as they have been prescribed by their personal physician. If necessary, the trainer will contact 9-1-1. All personal trainers will be required to have completed CPR certification (BLS).

Included in the training of our professional personal trainers will be for them to be aware of and familiar with asthma signs and symptoms (please note that this is more training that coaches typically receive). All trainers will tell the participant to let him/her know if they are experiencing symptoms. Before each training session begins, the trainer will ensure that the participant has his/her bronchodilator readily available prior to beginning exercise activities. Should an exercise-induced bronchoconstriction episode occur, participants will be instructed to respond as they have been prescribed by their personal physician. If necessary, the trainer will contact 9-1-1. All personal trainers will be required to have completed CPR certification (BLS). Additionally, we will have an on call physician that can be reached if any problems occur or questions arise. Parents will be encouraged to accompany their children during the exercise session and remain near. **If the participant becomes uncomfortable, they will be instructed to stop the exercise at any point.** Trainers will be instructed not to push the children if they feel uncomfortable at any time.

If any emergencies should occur during these training sessions, the personal trainer will be instructed to call 9-1-1.

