### **NON-TECHNICAL SUMMARY**

Provide a non-technical summary of the proposed research project that can be understood by IRB members with varied research backgrounds, including non-scientists and community members. The summary should include a brief statement of the **purpose of the research** and **related theory/data supporting** the intent of the study as well as a brief description of the **procedure(s) involving human subjects**. *This summary should not exceed ½ page.*

The goal of this research is to determine whether 10-weeks of exercise training can benefit asthmatic children and young adults with a history of exercise-induced bronchoconstriction (EIB). Physical activity is a double-edged sword for children and adults with asthma. On the one hand, exercise is a common trigger of wheezing (EIA—exercise induced asthma), occurring in as many as 80% of affected individuals. On the other hand, exercise and fitness training seem to benefit asthma control. The underlying causes responsible for EIA remain unknown. We will, for the first time, test hypotheses focused on mechanisms of exercise training, asthma and Exercise Induced Bronchoconstriction that involve the genomic changes of circulating white blood cells. We will also study an exciting newly discovered aspect of gene expression regulation in the white blood cells known as epigenetics: a process that takes place when genomic changes happen as a result of exposure to the environment. Our study is based on emerging exciting new data from this and other laboratories demonstrating that (1) white blood cells play an important role in bronchoconstriction[1,2] in children, (2) gene and cytokine expression in circulating white blood cells are abnormal in asthma,[3,4] and (3) brief exercise may change genomic and inflammatory-profiles of these cells.[5-7] Each participant will undergo a training regimen. The participants will come to our lab up to three times before the beginning of the training program, and up to three times immediately at the end of the exercise program to perform Exercise Fitness Session and Exercise Challenge Sessions. The visits may occur in any order, depending on the availability of the laboratory and timing. In the Exercise Fitness Session, the participant will perform a standard exercise test to determine fitness and will perform a series of pulmonary function tests. In addition, the participants will have two DXA scans to determine body composition (prior to

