In the Field (Approximately 1 hour per session for up to 30 sessions)	Exercise-Training	
 
• Personal trainers, small-groups, community venues, tailored training sessions x 3 weekly
 

	Compliance	
 
Attendance at exercise sessions
 
Exercise intensity will be assessed using heart rate (HR) monitors
 

Week 6-7		
At Home	Actigraph	
 
Assessment of physical activity over 7 days
 

At Home	Saliva Collection	
 
3 times a day (3 samples) over two consecutive days
 

Week 11		
At Home	Actigraph	Assessment of physical activity over 7 days
At Home	Saliva Collection	3 times a day (3 samples) over two consecutive days
Weeks 12		
PERC/ICTS Lab: Fitness Assessment (Approximately 2 hours)	Clinical Assessment	
 
Clinical Evaluation
 
Vitals and anthropometric measures (blood pressure, temperature, height and weight)
 

	Progressive Exercise Testing	
 
Ramp type protocol to assess peak VO2 (aerobic fitness)
 
Pre- and post-exercise Exhaled NO measurements
 
Pre- and post-exercise PFTs
 
Pre- and post-exercise blood flow measurements
 
Pre- and post-exercise saliva collection
 

	DXA	
 
Body composition (lean and fat mass)
 

	Executive Function Test	
 
Executive function tasks – 5 min of specific computer games
 

PERC/ICTS Lab: Exercise Challenge (separate at least 48 hours from the Fitness Assessment visit) (Approximately 3 hours)	Exercise Challenge on a cycle ergometer (10 x 2-min bouts @ ~70% peak work rate, with 1-min intervals)	
 
Blood draw* (before, immediately after, and one-hour after the exercise challenge).
 
Pre- and post-exercise Exhaled NO measurements
 
Pre- and post-exercise PFTs
 
Pre- and post-exercise saliva collection
 

PERC/ICTS Lab: Exercise Challenge (Approximately 2 hours)	Exercise Challenge on a cycle ergometer (10 x 2-min bouts @ ~70% peak work rate, with 1-min intervals)	
 
Pre- and post-exercise blood flow measurements
 
Pre- and post-exercise PFTs
 

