## B. Statistical Analysis Plan

1. **Variables of Interest** - Clearly identify the primary outcome(s) and key factor(s) of interest.
2. **Statistical goal** - State the statistical goal(s) of the study (e.g., Comparison of group means, estimation of the proportion of success, estimation of variability for future study design, etc.).
3. **Statistical approach** - Describe the statistical approach(es) to be used to address the study's statistical goal(s) (e.g., T-test to compare means, confidence interval estimate(s), etc.). *Note: Required for ICTS SRC review.*
4. **Secondary analyses** - Clearly state any secondary analyses to be performed including secondary outcomes and comparison groups along with the statistical methods that will be used to perform the secondary analyses. *Note: Required for ICTS SRC review.*

***If a statistical analysis plan is not appropriate for your study design, please describe a non-statistical plan for assessing your study results.***

***Aim 1: Elucidate key abnormal genomic and epigenetic responses to brief exercise in leukocytes of children and adults with moderate-to-severe asthma.***

***Aim 2: Identify the effect of training on the key genomic and epigenetic exercise response mechanisms in leukocytes in children and adults with moderate-to-severe asthma.***

Genomic expression profile is the **primary outcome variable** for Aims 1 and 2. Gene expression data will be normalized, log-transformed, and quality-checked and filtered across all arrays from all study subjects. Pre- to end-exercise change and before- to after-training change will be calculated for each subject and each probe set. Probe sets that pass filtration and belong to

selected functional pathways will be examined for group difference using 2-sample t-test and further adjusted with false discovery rate (FDR) controlling adjustments as described by Benjamini and Hochberg.

Leukocyte cell-function profile is the **secondary outcome variable** for Aims 1 and 2. Each outcome variable will be treated as an individual hypothesis. The primary analysis will apply 2-sample t-test to examine group difference in exercise effect and in training effect. The secondary analysis will utilize mixed model to evaluate group difference in training and exercise effect together, adjusting for possible confounding factors such as gender, BMI percentile, and fitness level.

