**Aim 3:** *Assess the clinical impact of exercise training in children and adults with persistent asthma on: (a) exercise induced airway inflammation, (b) asthma control, and (c) cardiorespiratory fitness and muscle adaptation.*

Outcomes from Aim 3 are considered as secondary outcome variables. We will apply paired t-tests for before- to after-training change. Furthermore, we will employ linear regression model to examine the effect of covariates such as gender, asthma severity (ACQ), and lean muscle tissue response to exercise-training (as determined by DXA).

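### Training is given in small groups of 3-6, but the tests and power tables for training effects treat participants as independent

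*Protocol*

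**What the plan says.** - **Who trains.** The Non-Technical Summary says "Each participant will undergo a training regimen", so both asthma and control participants are trained.
- **How.** Section 3A, Training Sessions: "The training sessions will occur three times a week up to 10 weeks", "in small groups of 3-6 subjects". Table 1 repeats this: "Personal trainers, small-groups, community venues, tailored training sessions x 3 weekly".
- **Aims 1 and 2, gene expression (primary outcome).** Changes from before to after training are among the quantities calculated. Probe sets in "selected functional pathways will be examined for group difference using 2-sample t-test", followed by false discovery rate control.
- **Aims 1 and 2, leukocyte function.** "The primary analysis will apply 2-sample t-test to examine group difference in exercise effect and in training effect". A mixed model appears only as a secondary analysis: "The secondary analysis will utilize mixed model to evaluate group difference in training and exercise effect together". Its listed adjustments are gender, BMI percentile and fitness.
- **Aim 3 (clinical outcomes).** "We will apply paired t-tests for before- to after-training change", plus a regression on gender, asthma severity and DXA lean tissue response.
- **Sample size (Section 4A).** Tables 3 and 4 are built on t-tests of individual participants.

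No listed model term covers training group, trainer or venue, and no ICC or design effect appears. The protocol does not say whether training groups mix asthma and control participants, whether membership is fixed, or how many groups or trainers there will be.

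**The concern.** People who train together may share a trainer, a venue, activities and a stretch of calendar time between baseline and the week-12 tests. Their changes may then resemble each other more than those of people in different groups. A paired or two-sample t-test takes its standard error from the spread between individuals and ignores that resemblance.

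Two things are at stake. A training effect in Aim 3 could be declared more often than the nominal 5%. In Aim 2, the probe-set p-values that feed the false discovery rate step could be miscalibrated, in a direction that depends on how groups are made up. The power stated for training effects may also be optimistic.

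**Working it through.** **Inputs from the protocol.** Training-group size m = 3 to 6 (Section 3A). About 60 completers per diagnosis group in children and about 40 in adults (Section 4A). Two-sided t-tests (Table 4).

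**Assumed.** Two-sided alpha 0.05, which Table 4 does not print; stable training groups; an ICC of the change from 0.01 to 0.20.

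**Step 1: reproduce Table 4.** Exact noncentral-t power for independent participants gives, at 80% power and n = 40/50/60:

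| Test | Stated | Recomputed |
|---|---|---|
| Two-sample | 0.634 / 0.566 / 0.516 | 0.634 / 0.566 / 0.516 |
| Paired | 0.454 / 0.404 / 0.368 | 0.454 / 0.404 / 0.368 |

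The 70% and 90% rows also match, except for one apparent digit slip (two-sample, n = 50, 90%: 0.665 stated, 0.655 computed) that does not matter here. Table 4 is therefore a calculation for independent participants, with no clustering allowance built in.

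**Step 2: all members of a training group in the same analysed group.** This covers the paired test when every group member is analysed, and the two-sample test with single-diagnosis groups.

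- Design effect: DE = 1 + (m − 1) × ICC
- Actual type I error: 2 × [1 − Φ(1.96/√DE)]

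| ICC | DE, m = 3 to 6 | True SE / assumed SE | Type I error |
|---|---|---|---|
| 0.01 | 1.02-1.05 | 1.01-1.02 | 5.2-5.6% |
| 0.05 | 1.10-1.25 | 1.05-1.12 | 6.2-8.0% |
| 0.10 | 1.20-1.50 | 1.10-1.22 | 7.4-11.0% |
| 0.20 | 1.40-2.00 | 1.18-1.41 | 9.8-16.6% |

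Example: m = 6, ICC 0.05 gives DE = 1 + 5 × 0.05 = 1.25; 1.96/√1.25 = 1.753; type I error 8.0%. Simulation (20,000 runs, n = 60, m = 4 and 6) agrees: 6.6-8.0% at ICC 0.05 and 8.5-11.2% at 0.10 over the two tests.

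**Step 3: training groups half asthma, half control (m = 4 to 6).**

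- *Paired test in one diagnosis group.* Only m/2 analysed participants share a training group, so DE = 1 + (m/2 − 1) × ICC. At ICC 0.05 this is 1.05-1.10 (5.6-6.2%), and at 0.10 it is 1.10-1.20 (6.2-7.4%). Simulation: about 5.8% and 6.4-7.0%.
- *Two-sample test.* The shared component cancels in the asthma-control difference, so the true variance is about (1 − ICC) times the assumed one. Type I error is 2 × [1 − Φ(1.96/√(1 − ICC))] = 4.4% at ICC 0.05 and 3.9% at 0.10. Simulation: about 4.5% and 4.0%.

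**Step 4: power in the Step 2 setting, n = 60, at the effect size Table 4 gives for 80%.** Effective sample size is 60/DE: 54.5 to 48.0 at ICC 0.05, and 50.0 to 40.0 at 0.10.

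| ICC | Power with n/DE | Detectable effect, two-sample (stated 0.516) | Detectable effect, paired (stated 0.368) |
|---|---|---|---|
| 0.05 | 76-71% | 0.541-0.577 | 0.386-0.411 |
| 0.10 | 73-63% | 0.565-0.632 | 0.403-0.451 |

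With degrees of freedom taken from the number of training groups (60/m per diagnosis), power at ICC 0.05 is 75-67% for the two-sample test and 73-62% for the paired test.

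**The case against.** The strongest reply is that none of the conditions for harm is stated. The protocol does not say that groups stay together or keep one trainer and venue. Table 1 describes sessions as tailored, and resistance work progresses with individual strength. No ICC is given, and at 0.01 nothing of consequence happens. Outcomes are measured in laboratory visits, not as a group event. If training did nothing for anyone, a shared trainer could not correlate changes through training. A correlation under the null needs shared calendar or venue influences, or group effects that average to zero. The paired tests serve only Aim 3, whose outcomes are secondary, and random-effect structure is often left to a separate analysis plan.

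Much of this stands and limits the claim. A reader might infer that the error bars are too narrow for every training analysis. The protocol does not support that: the direction of the two-sample test, which carries the Aim 2 primary outcome, depends on an unstated group composition and reverses in evenly mixed groups. Nor does a paired test become liberal however groups are formed. At least two analysed participants must share a group.

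The objection does not remove the point. Section 3B itself commits to the t-tests, so the choice has not merely been left open, and Table 4 demonstrably assumes independence. An unknown direction is a reason to model the grouping.

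**Conclusion.** The point holds conditionally. The protocol delivers training in groups of 3-6, fixes tests that assume independence, and allows for grouping in neither the listed models nor the power tables. Given reasonably stable membership and a positive within-group correlation, the standard errors for training effects are wrong.

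- **Paired tests (Aim 3):** too liberal whenever two or more analysed participants share a group. At an assumed ICC of 0.05-0.10, type I error is about 6-11% if all group members are analysed and about 6-7% in half-and-half groups.
- **Two-sample test of training change (Aim 2):** about 6-11% with single-diagnosis groups, about 4-4.5% with evenly mixed groups.
- **Pre-training Aim 1 comparisons:** not affected.

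The ICC range is an assumption. Nothing in the protocol favours its upper end, and larger values are shown only for range. This is an inexpensive improvement to the analysis, not evidence that the planned results would be invalid.

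**What to change.** 1. State how training groups are composed and whether membership is fixed. Record training-group and trainer identity for each participant; the compliance items in Table 1 are attendance and heart-rate intensity only.
2. For every before-to-after-training analysis, use a linear mixed model on the change with a random intercept for training group, or cluster-robust errors with a small-sample correction.
3. For probe sets, treat training group as a random block with a within-block correlation. Do not enter it as a fixed factor: with single-diagnosis groups it would be aliased with diagnosis and remove the comparison.
4. State that Table 4 assumes independence, and show detectable effects over an assumed ICC range, as in Step 4.

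**Cost.** Some extra data recording and analysis work, wider intervals for the paired tests, and a less favourable stated power: a nominal 80% becomes roughly 62-75% at ICC 0.05 with cluster degrees of freedom. No study procedure changes.
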